4.2.3 Subgroup Analysis

Subgroup analyses of the primary end point will be conducted using an ANCOVA model. Treatment group will be included as a fixed effect, with age and baseline 24-hour mean PAC count as covariates. If a covariate is also used as a subgroup factor, it will be excluded from the analysis model. The difference between groups will be reported as the point estimate, along with its 95% CI and p value.

Subgroups (not limited to) will include:

- Sex (male, female)
- Baseline 24-hour mean PAC count (\geq 5000 beats/24h, $<$ 5000 beats/24h)
- Age (\geq 65 years, $<$ 65 years)
- Left atrial diameter (\geq 40 mm, $<$ 40 mm)

The interaction between treatment group and subgroup factors will be assessed to evaluate whether the treatment effect varies across subgroups. The subgroup analysis is exploratory, and p values will not be adjusted for multiple comparisons; therefore, the results should not be used for inferential purposes.

Forest plots will be generated to present the results of the subgroup analyses.

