4.2.1 Primary Efficacy Analysis

The primary end point—the percent change from baseline in the 24-hour mean PAC count at Week 6—will be evaluated with an analysis- of- covariance (ANCOVA) model. Treatment group will be included as a fixed effect, and age and baseline 24-hour mean PAC count will be included as covariates. The between- group effect will be reported as the least- squares mean difference with its two- sided 95% confidence interval (CI) and p value.

Least- squares mean percentage reductions in the 24-hour mean PAC count will be plotted for each scheduled visit to depict response trajectories in both treatment groups.

Missing-Data Handling

Missing values for the Week 6 primary end point will be addressed with multiple imputation.

- **Imputation Procedure** Twenty complete data sets will be generated separately within each treatment group with a Markov chain Monte Carlo (MCMC) algorithm (PROC MI, SAS; seed = 20240716).

- **Imputation Model Covariates** Age, baseline 24-hour mean PAC count, and the 24-hour mean PAC count at every post-baseline visit.

After imputation, the data sets from both treatment groups will be combined. Each imputed data set will be analyzed with the prespecified ANCOVA model for the primary end point. Results will be pooled according to Rubin's rules with PROC MIANALYZE (SAS) to yield the final least-squares mean treatment difference with its two-sided 95% CI and P value.

Sensitivity Analysis:

A mixed-effects model for repeated measures (MMRM) will be applied to the primary end point as a prespecified sensitivity analysis. The model will include treatment group, visit, and the treatment-by-visit interaction as fixed effects and age and the baseline 24-hour mean PAC count as covariates. Parameters will be estimated with restricted maximum likelihood, and denominator degrees of freedom will be determined with the Kenward–Roger approximation.

Within-participant variability will be modeled with an unstructured covariance matrix. If the model fails to converge, alternative covariance structures will be evaluated sequentially—heterogeneous Toeplitz, heterogeneous first-order autoregressive, heterogeneous compound symmetry, Toeplitz, first-order autoregressive, and compound symmetry—until convergence is achieved; the first structure that converges will be retained.

Results will be presented as the least-squares mean treatment difference with the corresponding two-sided 95% CI.

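### The subgroup models drop age or baseline PAC count when its two-category version defines the subgroup, giving up a little precision for no need

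*SAP*

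**What the plan says.** SAP 4.2.1 sets the primary model: an ANCOVA on percent change at Week 6 in which "age and baseline 24-hour mean PAC count will be included as covariates". SAP 4.2.3 starts the subgroup analyses from the same model: "Treatment group will be included as a fixed effect, with age and baseline 24-hour mean PAC count as covariates". It then adds the rule in question: "If a covariate is also used as a subgroup factor, it will be excluded from the analysis model".

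The listed subgroup factors are sex, baseline PAC count (cut at 5000 beats per 24 hours), age (cut at 65 years) and left atrial diameter (cut at 40 mm). Applied to that list, the rule gives:

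- sex and left atrial diameter: adjusted for age and baseline PAC count;
- age subgroups: adjusted for baseline PAC count only;
- PAC-count subgroups: adjusted for age only.

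The section also plans an interaction assessment: "The interaction between treatment group and subgroup factors will be assessed to evaluate whether the treatment effect varies across subgroups". It does not write out the model for it. On status it says: "The subgroup analysis is exploratory, and p values will not be adjusted for multiple comparisons". It adds that the results are not for inferential use, and it calls for forest plots.

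**The concern.** Dropping a covariate makes sense when it is the same variable as the subgroup factor, because it is then constant within the subgroup and cannot be fitted. Here the factor is a two-category version of a quantitative covariate. Knowing that a participant is under 65, or at or above 5000 beats, leaves much of the value unspecified, and the rule leaves that remainder unadjusted.

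Baseline PAC count may well matter for this outcome. It is the denominator of the percent change (SAP 3.1.1 and 4.2), and the plan uses it in the primary ANCOVA, the sensitivity MMRM, the imputation model and the randomisation strata.

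At stake is some precision in the age and PAC-count rows of the forest plot, and consistency of adjustment between those rows, the other rows and the overall result. If the rule also carries into the unwritten interaction model, those two interaction tests lose a little precision as well.

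**Working it through.** **1. The plan's own figure.** Inputs from SAP 1.3.2: reductions of 50% and 30% (difference 20 points), SD 35, one-sided alpha 0.025, 1:1 allocation, 15% dropout, 256 participants. Evaluable per arm: 128 × 0.85 = 108.8, taken as 108. SE = 35 × √(2/108) = 4.76. Power = Φ(20/4.76 − 1.96) = Φ(2.24) = 98.7%. With all 128 per arm, SE = 35 × √(2/128) = 4.375 and power = 99.5%. The stated power of more than 95% reproduces. It uses no covariate adjustment, so the subgroup rule does not touch it.

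**2. Is the exclusion needed?** Eligibility runs from 18 to 80 years (Protocol 4.1), so the younger category covers 18 to 64 and the older 65 to 80. No upper limit on PAC count is given for the category at or above 5000. For the lower category, the entry threshold of 1000 applies to a 24-hour screening recording, while the covariate is a 24-hour mean from the 72-hour baseline recording, so 1000 is not a guaranteed floor. In every category the value varies, and it can be fitted together with the category.

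Reading the covariates as continuous is an inference, since the SAP does not use that word for them. It is the natural one: 4.2.1 and 4.2.3 name them without cut-points, whereas the Cochran–Mantel–Haenszel test in 4.2.2 spells the categories out.

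**3. Size of the loss.** Without the covariate, the subgroup SE is larger by the factor 1/√(1 − r²), where r is the covariate–outcome correlation inside the category. The documents give no correlation, so an overall value ρ is assumed. Cutting a simulated normal covariate (one million draws) at its median or its 70th percentile gives r. For the interaction the factor is √((1 − R²)/(1 − ρ²)), with R² the share of outcome variance explained by the category alone. This assumes that the exclusion carries over to the interaction model.

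| Assumed ρ | r within category | Subgroup SE larger by | Interaction SE larger by |
|---|---|---|---|
| 0.1 | 0.05–0.07 | 0.2–0.3% | 0.2% |
| 0.2 | 0.11–0.14 | 0.6–1.0% | 0.8–0.9% |
| 0.3 | 0.16–0.22 | 1.3–2.4% | 1.8–2.1% |
| 0.5 | 0.29–0.38 | 4.4–7.9% | 5.9–6.9% |

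Example: ρ = 0.5 with r = 0.376 gives 1/√(1 − 0.141) = 1.079. For the interaction at ρ = 0.3 with a median cut, R² = 0.0569 and √(0.9431/0.91) = 1.018.

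**4. In percentage points.** Assume a subgroup holding half the evaluable participants, 54 per arm, with SD 35. The 95% CI half-width without the covariate is 1.96 × 35 × √(2/54) = 13.2. With it, the half-width is multiplied by √(1 − r²): 12.9 at r = 0.2 and 12.6 at r = 0.3, a gain of 0.3 to 0.6 points.

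**5. Bias.** In 4,000 simulated subgroups of 108 participants with a true difference of 20, the mean estimates without and with the covariate were 20.08 and 20.07 (ρ = 0.2), 19.88 and 19.89 (0.3), and 19.98 and 20.00 (0.5). Neither analysis is biased.

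**6. Cost of the retained term.** The table uses the large-sample formula. Estimating one slope inflates the variance by about 1/(N − 4) = 1/104 at N = 108, or about 0.5% on the SE. The simulated SDs reflect this: 6.69 in both analyses at ρ = 0.2, 6.45 against 6.37 at 0.3 (1.4% larger without the covariate), and 6.26 against 5.91 at 0.5 (5.8% larger). At ρ of 0.1 to 0.2 the net gain is close to nil.

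**The case against.** The strongest reply is that very little depends on this. The section declares the analysis exploratory and not for inference. One covariate is lost in two of four listed analyses, the other stays, and the primary ANCOVA and testing hierarchy are untouched. All of that stands, and it sets the weight of the point. It does not supply a reason for the exclusion.

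Three stronger readings are tempting, and the documents do not support them.

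- *A reader might infer that the rule exposes these subgroups to imbalance or bias.* Age and PAC count at these same cut-points are the randomisation strata (Protocol 3.3.1, SAP 1.3.3), so the comparison within each category is randomised within strata. Only chance imbalance inside a category remains, and step 5 shows no bias.
- *A reader might infer that the age and PAC-count rows cannot be compared with the others.* In a linear model for a mean difference under randomisation, adjusted and unadjusted estimates target the same quantity. The rows differ in adjustment and slightly in precision, not in what they estimate.
- *A reader might infer intervals 5% to 15% wider.* That needs within-category correlations of 0.3 to 0.5. Nothing in the documents supports values that high, and cutting a covariate lowers its correlation within each category. Because the endpoint is already divided by baseline, the remaining correlation could be small.

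**Conclusion.** The point holds as a small loss of efficiency. The rule removes age or baseline PAC count from the two subgroup analyses whose categories are built from them, although the quantitative value still carries information there and nothing elsewhere in the SAP restores it. The estimates remain randomised and unbiased. The SE is larger by about 0.2% to 2.4% for an assumed overall correlation of 0.1 to 0.3, and by about 4% to 8% at 0.5, before allowing for the cost of estimating the slope. These figures rest on an assumed correlation, a normal covariate and cuts at the median or 70th percentile, none of which the documents give. The second consequence is that two sets of forest-plot rows are adjusted differently from the primary model. Importance is minor: this is an improvement worth making because it is nearly free, not an error that threatens a conclusion.

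**What to change.** Replace the exclusion sentence in SAP 4.2.3 with: *Age and baseline 24-hour mean PAC count, as continuous covariates, are retained in every subgroup model; the interaction model adds the subgroup indicator and its interaction with treatment.*

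This aligns every forest-plot row with the primary adjustment, settles that the covariates are continuous, and specifies the interaction model, which the section now leaves open. It needs no new data. The cost is that short piece of added specification and one degree of freedom in each affected model, negligible unless a subgroup is very small.

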4.3 Safety Analysis

4.3.1 Drug Exposure

Based on the SS, the following information will be summarized by treatment group and presented in tabular form for all study drug administration data:

- Exposure duration (days) = Last dose date during the treatment period - First dose date during the treatment period + 1
- Actual total dose administered (mg) = Total dose actually administered during the study period
- Actual dose intensity (mg/day) = Actual dose administered (mg) / Exposure duration (days)

- Compliance (%) = (Actual dose intensity (mg/day) / Planned dose intensity (mg/day)) × 100%

Planned dose intensity (mg/day) = $(7 \times 10 \text{ mg} + 35 \times 20 \text{ mg}) / 42$

4.3.2 AE

AEs will be summarized by treatment group in the safety population. Events will be coded with the MedDRA and classified by severity (mild, moderate, or severe). A TEAE is any AE that begins after the first study dose or worsens in severity relative to its pre-dose state; events with an indeterminate temporal relationship to dosing will also be considered TEAEs. All TEAEs will be individually listed, and their incidence will be tabulated and summarized descriptively.

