5.2 Dosing Regimen

Beginning on Day 1, participants in both the memantine and placebo groups will receive one-half tablet (5 mg) twice daily for 7 days. From Week 2 onward, the dose will be increased to one tablet (10 mg) twice daily and continued through the end of Week 6. The complete dosing schedule is summarized in Table 1.

Participants assigned to either memantine or matching placebo will follow a two-step, twice-daily schedule:

Table 2 Dosing Regimen

Study Week	Dose per administration	Total daily dose	Administration details*
Week 1	½ tablet (5 mg)	10 mg	Orally, at consistent morning and evening times (recommended interval, 12 h ± 2 h)
Weeks 2 – 6	1 tablet (10 mg)	20 mg	Orally, at consistent morning and evening times (recommended interval, 12 h ± 2 h)

* Each active tablet contains 10 mg memantine. Placebo tablets are identical in appearance, weight, packaging, and schedule but contain no active ingredient. The planned treatment duration is 42 – 45 days.

Dose Modification

The investigator may reduce the dose, interrupt treatment, or permanently discontinue the investigational product under the circumstances outlined below.

Dose Reduction — If a *moderate* AE occurs during the treatment phase and the investigator has ruled out causes unrelated to the study drug, the dose may be reduced from 1 tablet twice daily (BID) to $\frac{1}{2}$ tablet BID for 3 to 7 days. Should the AE lessen or resolve, the investigator may reinstate the full dose of 1 tablet BID.

Temporary Interruption — If a *moderate* AE occurs during the run-in period and substantially interferes with daily activities or work, and the investigator has ruled out non-drug-related causes, study treatment may be withheld for 3 to 7 days. Should the AE diminish or resolve, the participant may, at the investigator's discretion, re-enter the run-in phase and resume dosing as specified in the protocol.

Permanent Discontinuation — If a severe AE or SAE occurs after randomization, the investigator must instruct the participant to stop all study medication immediately and retrieve any unused investigational product and its packaging. The participant is to receive appropriate medical care, and the event must be documented in detail in the electronic case-report form.

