5.4 Investigational Product Accountability

Designated pharmacy personnel at each study site are responsible for the receipt, storage, dispensing, and reconciliation of all investigational product (IP). Complete, contemporaneous documentation must be maintained throughout the trial.

Table 3 Study Drug Handling and Accountability

Process	Requirements
Receipt	Upon delivery, the site pharmacist (or authorized designee) verifies the shipment against the packing list, completes and signs the drug-receipt form, and documents the date of receipt.
Storage	IP must be stored in a locked, access-controlled cabinet under the temperature conditions specified on the label (10 – 30 °C). Storage and handling procedures must comply with all applicable regulations.
Dispensing	IP is dispensed according to each participant's randomization number and corresponding kit number, as assigned by the IRT system.
Reconciliation	For every kit, the following details must be entered promptly and indelibly in the drug-accountability log: date dispensed, quantity issued, kit number, participant randomization number, return of empty packaging, and quantity of unused tablets returned or destroyed.
Inspection	All IP accountability records are subject to review by study monitors, auditors, and regulatory inspectors. Any discrepancies must be documented, investigated, and resolved in accordance with the sponsor's standard operating procedures.

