1.3 Study Design

1.3.1 Overall Design

This investigator-initiated, multicenter, randomized, double-blind, parallel-group, placebo-controlled trial will enroll 256 adults (18–80 years of age) with frequent symptomatic PACs.

After an initial eligibility screen, all candidates will undergo 72-hour continuous patch-based ambulatory electrocardiographic monitoring to quantify baseline PAC burden. Participants who meet the inclusion criteria will be randomly assigned on Day 0, in a 1:1 ratio, to receive oral memantine or matched placebo. Randomization will be stratified according to age (≥ 65 vs. < 65 years) and baseline PAC burden (≥ 5000 vs. < 5000 PACs per 24 hours), yielding 128 participants per group (total, 256).

The protocol specifies five visits:

- Visit 1 (Screening; ≤ 14 days before randomization)—Baseline clinical assessments and 72-hour ambulatory ECG monitoring.
- Visit 2 (Day 7 ± 2 days)—Telephone contact to assess treatment adherence and solicit adverse events (AEs).
- Visit 3 (Day 28 ± 3 days), Visit 4 (Day 42 ± 3 days; end of treatment), and Visit 5 (Day 56 ± 3 days; end of study) — On-site evaluations, each including repeat 72-hour ambulatory ECG monitoring.

A schematic of the study procedures is provided in Figure 1.

[figure not shown]

Figure 1 Study Design Flowchart

The treatment phase will last 42 to 45 days. Seventy- two- hour ambulatory ECG will be initiated on study days 25–28 for Visit 3 (V3), days 39–42 for Visit 4 (V4), and days 53–56 for Visit 5 (V5). For V4, monitoring must begin 72 hours before the final scheduled dose; thus, if dosing concludes on day 42, monitoring must start on day 39. Conversely, if monitoring is initiated on day 42, study medication must continue through day 45. All other assessments scheduled for V3 – V5 must be completed between placement and removal of the 72- hour ECG device.

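### The SAP's compliance percentage compares each participant's own average daily dose with a fixed 42-day average, so a participant who misses nothing scores 100% only at exactly 42 days

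*SAP*

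**What the plan says.** SAP 4.3.1 builds the measure in three steps. Exposure is specific to the participant: "Exposure duration (days) = Last dose date during the treatment period - First dose date during the treatment period + 1". The daily average is taken over that interval: "Actual dose intensity (mg/day) = Actual dose administered (mg) / Exposure duration (days"). Compliance is then "Compliance (%) = (Actual dose intensity (mg/day) / Planned dose intensity (mg/day")) times 100. The planned intensity is the same for everyone: 7 days at 10 mg plus 35 days at 20 mg, divided by 42. All of this is summarized by treatment group in the safety set.

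The schedule behind it is in Protocol 5.2: "Beginning on Day 1, participants in both the memantine and placebo groups will receive one-half tablet (5 mg) twice daily for 7 days", then one 10 mg tablet twice daily from Week 2. SAP 1.3.1 does not fix the length at 42 days: "The treatment phase will last 42 to 45 days". Protocol 5.2 also provides for departures from the full schedule. After a moderate adverse event, "the dose may be reduced from 1 tablet twice daily (BID) to" half a tablet twice daily for 3 to 7 days. Interruptions of 3 to 7 days are possible. Stopping is mandatory in some cases: "If a severe AE or SAE occurs after randomization, the investigator must instruct the participant to stop all study medication immediately".

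Protocol 7.3.5 promises a description of adherence by arm but gives no formula, and Protocol 7.3.2 gives the SAP precedence. SAP 4.3.1 is thus the only definition.

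**The concern.** A compliance percentage is normally read in one of two ways: doses taken out of doses due while on drug, or the share of the planned course received. This formula gives neither. Because the first week is scheduled at half the later daily dose, anyone who stops early has a low daily average by design, and the formula reports that as poor compliance.

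Early stopping may well differ between arms, because severe or serious adverse events force discontinuation. If it does, the compliance row will differ between arms even when every participant took every scheduled dose until stopping. A reader using that row to judge whether treatment was taken cannot tell early stopping from missed doses. Nor does the SAP say whether a reduction or interruption that the protocol allows counts against the participant.

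**Working it through.** **Inputs.** 10 mg/day on Days 1–7 and 20 mg/day from Day 8 (Protocol 5.2); exposure, intensity and compliance formulas and the 42-day constant (SAP 4.3.1); planned duration of 42–45 days (SAP 1.3.1).

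**The SAP's denominator.** 7×10 + 35×20 = 770 mg; 770/42 = 18.33 mg/day. This matches the protocol schedule exactly.

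**Full adherence to day d.** Dose = 10×min(d, 7) + 20×max(d − 7, 0). For d > 7 the daily average is (20d − 70)/d = 20 − 70/d, which rises with d. Setting 20 − 70/d = 18.33 gives d = 70/1.667 = 42, the only solution. For d ≤ 7 the average is 10 mg/day and never reaches 18.33.

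| Last day, no dose missed | Dose (mg) | mg/day | SAP compliance | Share of 770 mg |
|---|---|---|---|---|
| 7 | 70 | 10.00 | 54.5% | 9.1% |
| 14 | 210 | 15.00 | 81.8% | 27.3% |
| 21 | 350 | 16.67 | 90.9% | 45.5% |
| 28 | 490 | 17.50 | 95.5% | 63.6% |
| 35 | 630 | 18.00 | 98.2% | 81.8% |
| 42 | 770 | 18.33 | 100.0% | 100.0% |
| 45 | 830 | 18.44 | 100.6% | 107.8% |

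**Different histories, same score.** A 42-day course is 7×1 + 35×2 = 77 tablets. A completer who misses 7 full-dose tablets takes 700 mg, and 700/42 = 16.67 mg/day, or 90.9%. That equals the score of the Day-21 stopper who missed nothing. A 42-day course with a 7-day reduction from 20 to 10 mg/day also totals 700 mg and scores 90.9%; with a 3-day reduction it is 740/42/18.33 = 96.1%.

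**Possible shift in an arm mean.** The documents give no stopping rates or times, so these are assumptions. Stoppers take every dose until stopping, and the others score 100%.

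- The shortfall of a perfect stopper is 45.45 points for d ≤ 7 and 381.82/d − 9.09 points for d = 8 to 41.
- With stop days uniform over Days 1–41, the first seven days contribute 7×45.45 = 318.2 and the other 34 contribute 343.8. The mean is 662.0/41 = 16.1 points.
- Multiplied by the difference in stopping rates:

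| Stopping, one arm vs the other | Uniform over Days 1–41 | All in Days 1–7 |
|---|---|---|
| 10% vs 5% | 0.8 points | 2.3 points |
| 15% vs 5% | 1.6 points | 4.5 points |
| 20% vs 5% | 2.4 points | 6.8 points |

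**The case against.** The strongest reply is that little depends on this number. The table is descriptive. Per-protocol membership turns on major deviations, and neither document sets a compliance cut-off. No efficacy result changes. Participants who finish in the planned 42–45 days are off by 0 to 0.6 points. Exposure duration and total dose sit in the same table, and SAP 4.1.1 reports discontinuations by reason, so shortened courses will not be hidden. All of that stands, and it limits the weight of the point.

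It can also be said that the ratio is a well-defined relative dose intensity with an unsuitable label. That is fair as a description, but the SAP calls it compliance and offers no other measure of adherence. The neighbouring rows show that a course was short; they do not show whether doses were missed.

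Two narrower objections also stand. The dose-reduction example lies at exactly 42 days, so it illustrates an unstated counting rule rather than the fixed denominator. The largest arm-level shift needs every stop to fall in the first week, which nothing in the documents supports; it is the far end of a range. Finally, any single ratio loses information: adherence on drug would score a perfect Day-7 stopper and a perfect completer alike at 100%. That is why two rows are needed.

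**Conclusion.** The concern holds. As written, the formula scores a participant with no missed dose at anything from 54.5% to 100.6%, depending only on when treatment ended, and it is right only at 42 days. This follows from the documents' own schedule and formula, assuming full daily doses on both the first and the last dosing day. For completers the error is negligible; for early stoppers it is large. The effect on an arm mean depends on assumed stopping patterns: 0.8 to 2.4 points with stops spread evenly over Days 1–41, and up to 6.8 points if all fall in Week 1. The consequence is a misleading descriptive comparison of adherence, with no documented route into the efficacy conclusions. It should be corrected, but it does not threaten the trial.

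**What to change.** In SAP 4.3.1, define compliance as tablets taken divided by tablets scheduled under the current protocol between that participant's first and last dose dates, times 100. Count tablets in both arms, which also avoids relying on nominal milligrams for placebo. Add a separate row for the percentage of the full planned course received, with 77 tablets for 42 days and 7×1 + 38×2 = 83 for 45 days. A Day-21 stopper who missed nothing then shows 100% adherence on drug and 35/77 = 45.5% of the course.

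State also whether permitted reductions and interruptions lower the scheduled count. A 42-day course with a 7-day reduction is 70/77 = 90.9% if they do not and 70/70 = 100% if they do. Because Protocol 5.2 lets an interrupted participant go back to the run-in phase, say how the scheduled count is derived after such a restart.

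The cost is one replaced formula, one extra derived row and a small programming change. Protocol 5.4 already requires the quantity issued to be logged for each kit, together with "return of empty packaging, and quantity of unused tablets returned or destroyed", so no new data collection is needed.
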